**Table 14 Analysis Strategy for Safety Parameters**

Safety Tier	Safety Endpoint	p-Value	95% CI for Treatment Comparison	Descriptive Statistics
Tier 2	Any AE		X	X
	Any Grade 3-5 AE		X	X
	Any Serious AE		X	X
	Any Drug-Related AE		X	X
	Any Serious and Drug-Related AE		X	X
	Any Grade3-5 and Drug-Related AE		X	X
	Dose Modification due to AE		X	X
	Discontinuation due to AE		X	X
	Death		X	X
	Specific AEs, SOCs (including $\geq 4$ of subjects in one of the treatment groups)		X	X
Tier 3	Specific AEs, SOCs (incidence $< 4$ of subjects in all of the treatment groups)			X
	Change from Baseline Results (Labs, ECGs, Vital Signs)			X

**8.6.3 Statistical Methods for Patient Reported Outcome (PRO) Analyses: EORTC QLQ-C30 and EORTC QLQ-STO22**

Changes in health-related quality-of-life assessments from baseline using the EORTC QLQ-C30 and EORTC QLC-STO22 will be evaluated using a constrained longitudinal data analysis (cLDA) model.

Time to deterioration (10 points worse than baseline) in EORTC QLQ-C30 global health status, nausea/vomiting symptom, appetite loss symptom, and QLQ-STO22 abdominal pain/discomfort symptom will be analysed using the same methods used for the primary endpoint, PFS (stratified Cox model and Kaplan Meier plot). Rate of improvement (10 points better than baseline) for these endpoints will be analysed using the same method used for ORR (ie stratified Miettinen and Nurminen’s method).

Details of PRO analyses will be described in the sSAP.

**8.6.4 Summaries of Baseline Characteristics, Demographics, and Other Analyses**

**8.6.4.1 Demographic and Baseline Characteristics**

The comparability of the treatment groups for each relevant characteristic will be assessed by the use of tables and/or graphs. No statistical hypothesis tests will be performed on these characteristics. The number and percentage of subjects randomized, and the primary reason for discontinuation will be displayed. Demographic variables (such as age) and baseline

characteristics will be summarized by treatment either by descriptive statistics or categorical tables.

## **8.7 INTERIM ANALYSES**

### **8.7.1 Safety Interim Analysis**

An interim safety analysis will take place after 10 subjects in each treatment arm have completed 1 cycle of therapy. Interim periodic safety monitoring will include review of AE data by the eDMC as specified in the DMC charter.

### **8.7.2 Efficacy Interim Analyses**

There are two interim analyses planned in this study. The first interim analysis (IA1) will take place when all subjects are enrolled and followed for 10 months and at least 317 OS events are observed across the pembrolizumab in combination with SOC and SOC arms, in subjects with PD-L1 CPS1. The second interim analysis (IA2) will take place after a minimum of 16 months follow-up and at least 369 OS events are observed across the pembrolizumab in combination with SOC and SOC arms, in subjects with PD-L1 CPS1. In order to account for potential delayed treatment effect, which was observed with immunotherapy study data external to this study, the final analysis (FA) will be 22 months after the last subject is randomized and approximately 415 OS events are observed across the pembrolizumab in combination with SOC and SOC arms, in subjects with PD-L1 CPS1 [48; 49; 50]. The additional follow-up time is incorporated into the trial to ensure that the final analysis is conducted at an appropriate time to characterize the potential benefit of immunotherapy, where the treatment effect is most pronounced towards the tail of the survival curve. [Table 15](#) summarizes the key features of the interim analysis.

For PFS (H1) and OS (H2, H3, H5, and H6), a Hwang-Shih-DeCani alpha-spending function with gamma parameter (-4) is used to construct group sequential boundaries to control the type I error rate. For OS (H4 – NI monotherapy vs. SOC in the CPS1 population), a Hwang-Shih-DeCani alpha-spending function with gamma parameter (-15) is used to construct group sequential boundaries to control the type I error rate.

For H2, the actual boundaries and the alpha level will be determined from the number of events observed at the time of the interim analyses using the corresponding alpha-spending function. The boundary for the final analysis will be adjusted according to the actual alpha spent at the IAs and the actual number of events observed at the IA and FA.

For H1, H3, H4, H5, and H6, since the timing of the IAs are not driven by these hypotheses; alpha is spent as a function of the minimum of the actual event information fraction and the expected event information fraction. This ensures that the actual spending will be no more aggressive than the planned, while at the same time ensuring that not all alpha is spent prior to final planned event counts. If events accrue more slowly than expected or the same as expected, spending will be based on actual information fraction. If events accrue more quickly than expected, cumulative spending based on the expected information fraction will be used in order to save some alpha for analyses that will be performed with more than the

originally planned maximum events. For example, at IA1 for H3, if 125 OS events have occurred (ie, more than the expected 111 OS events), the alpha spending at IA1 will be according to the expected information fraction ( $111/147 = 76\%$ ) instead of the actual information fraction ( $125/147 = 85\%$ ).

Table 15 summarizes the timing, sample size, and decision guidance of the interim analyses and FA. Bounds are based on estimated number of events and the alpha allocated at the design stage of the study and will be updated at the time of the analyses using the observed number of events, the alpha re-allocation and spending functions as noted above.

Table 15 Decision Guidance at Each Efficacy Analysis

Analysis	Criteria for Conduct of Analysis	Testing	Value	Efficacy
Interim Analysis 1 (Interim OS analysis/ PFS analysis)	10 months after last subject randomized and at least 317 OS events in the combination arm and SOC arm, in subjects with PD-L1 CPS1 whichever comes later	PFS (H1) : pembrolizumab in combination with SOC vs. SOC, in subjects with PD-L1 CPS1	p value (1-sided)	$\leq 0.0007$
			~ HR at bound (~ 389 events)	0.723
		OS (H2): Pembrolizumab in combination with SOC vs. SOC in subjects with PD-L1 CPS1	p value (1-sided)	$\leq 0.0047$
			~ HR at bound (~317 events)	0.747
		OS (H3): Pembrolizumab in combination with SOC vs. SOC in subjects with PD-L1 CPS10	p value (1-sided)	$\leq 0.0027$
			~ HR at bound (~111 events)	0.590
		OS (H4): Non-inferiority of Pembrolizumab mono therapy vs. SOC in subjects with PD-L1 CPS1	p value (1-sided)	$\leq 0.0001$
			~ HR at bound (~ 317 events)	0.7935
		OS (H5): Pembrolizumab mono therapy vs. SOC in subjects with PD-L1 CPS1	p value (1-sided)	$\leq 0.0015$
			~ HR at bound (~ 317 events)	0.717
		OS (H6): Pembrolizumab mono therapy vs. SOC, in subjects with PD-L1 CPS10	p value (1-sided)	$\leq 0.0027$
			~ HR at bound (~ 112 events)	0.592

Analysis	Criteria for Conduct of Analysis	Testing	Value	Efficacy
Interim Analysis 2 (Interim OS analysis/ Final PFS analysis)	16 months after the last subject is randomized and at least 369 OS events are observed in the Combination arm and SOC arm, whichever comes later	PFS (H1): pembrolizumab in combination with SOC vs. SOC, in subjects with PD-L1 CPS1	p value (1-sided)	$\leq 0.0007$
			~ HR at bound (~430 events)	0.735
		OS (H2): Pembrolizumab in combination with SOC vs. SOC, in subjects with PD-L1 CPS1	p value (1-sided)	$\leq 0.0063$
			~ HR at bound (~ 369 events)	0.771
		OS (H3): Pembrolizumab in combination with SOC vs. SOC, in subjects with PD-L1 CPS10	p value (1-sided)	$\leq 0.0037$
			~ HR at bound (~130 events)	0.624
		OS (H4) Non-inferiority: Pembrolizumab vs. SOC, in subjects with PD-L1 CPS1	p value (1-sided)	$\leq 0.0007$
			~ HR at bound (~ 369 events)	0.862
		OS (H5) superiority: Pembrolizumab vs. SOC, in subjects with PD-L1 CPS1	p value (1-sided)	$\leq 0.0019$
			~ HR at bound (~ 369 events)	0.740
		OS (H6) superiority: Pembrolizumab vs. SOC, in subjects with PD-L1 CPS10	p value (1-sided)	$\leq 0.0037$
			~ HR at bound (~ 131 events)	0.626

Analysis	Criteria for Conduct of Analysis	Testing	Value	Efficacy
Final Analysis: OS analysis	22 months after the last subject is randomized and approximate 415 OS events are observed in the combination arm and SOC arm, in subjects with PD-L1 CPS1.	OS (H2): Pembrolizumab in combination with SOC vs. SOC, in subjects with PD-L1 CPS1.	p value (1-sided)	≤0.0099
			~ HR at bound (~ 415 events)	0.795
		OS (H3) Pembrolizumab in combination with SOC vs. SOC, in subjects with PD-L1 CPS10	p value (1-sided)	≤0.0058
			~ HR at bound (~ 147 events)	0.659
		OS (H4) non-inferiority pembrolizumab mono therapy vs. SOC, in subjects with PD-L1 CPS1	p value (1-sided)	≤0.0039
			HR at bound (~ 415 events)	0.925
		OS (H5) superiority: Pembrolizumab vs. SOC, in subjects with PD-L1 CPS1	p value (1-sided)	≤0.003
			~ HR at bound (~415 events)	0.763
		OS (H6) superiority: Pembrolizumab vs. SOC, in subjects with PD-L1 CPS10	p value (1-sided)	≤0.0058
			~ HR at bound (~ 148 events)	0.661

For ORR, the analysis population is subjects with 10 months follow up. Based on the current timing of IA1, all subjects will have 10 months follow-up by IA1. Interim analysis 1 will be the final analysis for ORR (H7).

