ML17032 study [36] compared cisplatin/capecitabine with cisplatin/5-FU. The primary objective was to show non-inferiority in terms of PFS time. Median PFS was 5.6 months among subjects receiving cisplatin/capecitabine and 5.0 months among subjects receiving cisplatin/5-FU; median OS times were 10.5 months and 9.3 months, and ORR were 46% and 32%, in these groups respectively. Based on this study, capecitabine has been approved in combination with a platinum-based regimen for the first-line therapy of advanced gastric cancer in US and Japan.

The SPIRITS study [37] was Phase 3 trial to compare the oral fluoropyrimidine S1 plus cisplatin vs S1 in Japanese subjects. Median OS was 13 months vs 11 months. PFS was 6 months vs. 4 months;  $p < 0.001$ ). Based on these data, S1 plus cisplatin became the most popular regimen for the first-line therapy of advanced gastric cancer in Japan.

The FLAGS trial [38] was phase 3 trial to compare the oral fluoropyrimidine S1 plus cisplatin vs 5-FU plus cisplatin in western population. The trial failed to show superiority for S1 plus cisplatin over 5-FU plus cisplatin; median OS was 8.6 months and 7.9 months, for S1/cisplatin and 5-FU/cisplatin, respectively. More toxicity of S1 and dose reduction due to AEs was observed in Western population.

In summary, platinum/fluoropyrimidine doublet regimens are the most broadly used for first-line chemotherapy regimen for advanced gastric cancer. The comparable efficacy of regimens substituting capecitabine for infused 5-fluorouracil has been directly studied in two phase III trials: the REAL-2 study and the ML17032 study. The combination of infused or oral 5-fluorouracil and cisplatin is therefore recognized worldwide as one of the standard first-line chemotherapy regimens for subjects with mGC.

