### 8.9 Sample Size and Power Calculations

The study will randomize approximately 750 subjects in a 1:1:1 ratio among the three treatment arms: pembrolizumab as monotherapy (mono therapy), pembrolizumab in combination with SOC (combination therapy), and SOC (control).

The study is event driven (ie, follow-up times are subject to change but number of events is not).

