**OS:**

At the FA, approximately 415 OS PD-L1 CPS1 (H2) events will be accumulated in the combination therapy arm and control arm. With 415 events, the study has ~91% power to detect a hazard ratio of 0.70 (pembrolizumab in combination with SOC vs. SOC) at alpha = 1.25% (one-sided). These calculations are based on the following assumptions: 1) OS follows an exponential distribution with a median of 10 months in the control arm, 2) an enrolment period of 19 months, and 3) a yearly dropout rate of 2%.

At the final analysis, approximately 147 OS-PD-L1 CPS10 (H3) events will be accumulated in the combination therapy arm and control arm. With 147 events, the study has ~ 80% (73%) power to detect a hazard ratio of 0.58(0.60) (pembrolizumab in combination with SOC vs. SOC in subgroup of subjects with PD-L1 CPS10) at alpha = 0.75% (one-sided)

For the monotherapy arm and the control arm, if there are 415 OS PD-L1 CPS1 events, the study has ~89% power to establish non-inferiority (H4) (NI margin =1.2) of pembrolizumab vs SOC (H4) at alpha=0.40% (one-sided) if HR = 0.82, and ~82% power (superiority, H5) to detect a HR = 0.70 at alpha = 0.40%. Following the FDA Guidance for Non-Inferiority Clinical Trials [52], the non-inferiority margin was based on retaining 50% of the control effect size (cisplatin and 5-fluorouracil vs. BSC), ie the lower bound of the confidence interval of the estimated control effect based on past studies. The control effect size is estimated as 0.67 based on Wagner 2006 [53]

At the final analysis, approximately 148 OS-PD-L1 CPS10 (H6) events will be accumulated in the pembrolizumab and control arm. With 148 events, the study has ~ 80% (63%) power to detect a hazard ratio of 0.58(0.63) (pembrolizumab vs. SOC in subgroup of subjects with PD-L1 CPS10) at alpha = 0.75% (one-sided)

The assumed median PFS and OS in the control arm are observed from standard of care in 1L treatment of gastric cancer [45] [46].

The sample size and power calculations were performed in the software EAST 5.4.

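### H2 (combination OS, CPS≥1) lacks the interim spending cap given to the other primary hypotheses, although calendar time also sets its interim looks, so alpha meant for the late final analysis can be used early

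*Combined protocol and SAP*

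**What the plan says.** Section 8.7.2 uses a Hwang-Shih-DeCani spending function with gamma −4 for H1, H2, H3, H5 and H6, and gamma −15 for H4. It then sets two rules for the interims.

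- **H2:** "the alpha level will be determined from the number of events observed at the time of the interim analyses". The final boundary is adjusted for what has been spent and for the actual event counts. Nothing sets a ceiling on interim spending.
- **H1 and H3 to H6:** spending uses the smaller of the actual and the expected information fraction, because these hypotheses do not drive the interim timing. One stated aim is "ensuring that not all alpha is spent prior to final planned event counts".

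Table 15 makes each interim wait for two conditions, whichever is met later. IA1 needs 10 months after last randomisation and at least 317 H2 events. IA2 needs "16 months after the last subject is randomized and at least 369 OS events are observed". The final analysis (FA) is placed at 22 months and about 415 events, and Section 8.7.2 justifies the extra follow-up by a possible delayed effect of immunotherapy.

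**The concern.** H2 is exempt from the cap on the premise that its own events decide when the interims happen. The triggers do not work that way. When the calendar minimum is the later condition, H2 events keep accruing past 317 and 369 until it is met, and an uncapped rule spends alpha on the surplus. Shorter control survival or a weaker treatment effect both speed up events.

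H2 carries the largest initial share of alpha (1.25% one-sided). If that alpha is largely or wholly spent by IA2, the 22-month analysis, which exists to catch a late-emerging effect, has little or no H2 test left. That is the situation the cap was written to prevent for the other five primary hypotheses.

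**Working it through.** **Inputs.** H2 alpha is 0.0125 one-sided (Sections 8.8 and 8.9). Section 8.9 gives the final count: "At the FA, approximately 415 OS PD-L1 CPS1 (H2) events will be accumulated in the combination therapy arm and control arm". It also gives the sample: "The study will randomize approximately 750 subjects in a 1:1:1 ratio among the three treatment arms", hence about 250 per arm. Control OS is exponential with median 10 months, enrolment takes 19 months, yearly dropout is 2%, and the design HR is 0.70. Two assumptions are mine. Accrual is uniform, and the H2 information fraction is events/415. The text gives no H2 denominator, but its H3 example divides by the planned final count (111/147).

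**Step 1: reproduce the plan.** Cumulative spending at fraction t is 0.0125 × (1 − e^(4t))/(1 − e^4).

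- IA1: t = 317/415 = 0.764, so 37.7% is spent (0.0047).
- IA2: t = 369/415 = 0.889, so 63.5% is spent (0.0079).
- Solving for the boundaries, with HR at bound = exp(−2z/√events), gives p bounds of 0.0047, 0.0063 and 0.0099 and HRs of 0.747, 0.771 and 0.795. These match Table 15. Power at HR 0.70 is 91.1%, against about 91% stated.

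**Step 2: which trigger comes later?** For hazard λ, dropout hazard δ and analysis time T from the start of enrolment, expected deaths per arm are

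250 × λ/(λ+δ) × {1 − [e^(−(λ+δ)(T−19)) − e^(−(λ+δ)T)] / [19(λ+δ)]}.

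At IA2, T = 19 + 16 = 35 and δ = −ln(0.98)/12 = 0.00168.

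- Control: λ = ln2/10 = 0.0693, giving 201 deaths.
- Combination: λ = 0.0485, giving 172 deaths.
- Total: 373. The same formula gives 326 at 10 months and 406 at 22 months.

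So on the design assumptions the event minimum (317, 369) is reached before the calendar minimum at both interims. The calendar sets the timing.

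**Step 3: uncapped spending when events run ahead.**

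| Control median, HR | H2 events at 10/16/22 months | H2 alpha spent by IA2 |
|---|---|---|
| Plan (Table 15) | 317/369/415 | 63.5% |
| 10 months, 0.70 | 326/373/406 | 66% |
| 10 months, 0.85 | 343/389/421 | 78% |
| 9 months, 0.80 | 355/401/430 | 87% |
| 8 months, 0.80 | 374/417/444 | 100% |

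With the cap, no row could exceed 63.5%, so at least 36.5% (0.0046) would remain for the FA.

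**Step 4: proportional hazards.** Take 380/415/440 events, where the uncapped rule spends everything by IA2.

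- HR 0.70: power 91.3% uncapped, 93.1% capped.
- HR 0.80: power 50.4% uncapped, 53.5% capped.
- Type I error is 0.0125 either way.

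**Step 5: delayed effect.** I assume HR 1 for 4 months and 0.65 afterwards, with the protocol's 2% dropout.

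- Median 9: about 391 events at IA2 and 79% spent. Two simulations gave power of 75.0% versus 76.6% capped, and 77.0% versus 78.3%.
- Median 8: about 408 events and 94% spent. The FA p bound is about 0.0066 (0.0064 to 0.0066 across runs) versus 0.0109 capped. Power was 73% versus 77%, and 72.1% versus 76.3%. About 23% of runs had 415 or more events by IA2.
- Median 10: the difference is about half a point.

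**The case against.** Spending on observed events is standard for the hypothesis whose counts set the triggers, and Section 8.7.2 adjusts the final boundary accordingly. Section 8.9 calls the study event driven. Reaching 415 events early means that the planned information has been reached, and power at the design HR of 0.70 is kept. The 10-month control median lies inside the spread cited in the protocol. Section 4.2.2.1 reports, for one Western trial, "median OS was 8.6 months and 7.9 months, for S1/cisplatin and 5-FU/cisplatin, respectively", but it also gives 10.5 months for cisplatin/capecitabine, and Section 4.1.4 gives 11.1 months for a chemotherapy control in HER2-positive disease. The delayed-effect scenario is not taken from the plan.

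Much of this stands, and it limits the point to a modest one. It does not remove it. Section 8.7.2 and Table 15 require a calendar minimum as well as events, so the exemption's premise fails even on the design assumptions. The 78% row also needs no short control median, only a weaker effect.

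Four stronger readings are tempting but unsupported:

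- **Type I error is inflated.** It is not. Total H2 error stays at 1.25% with or without the cap.
- **The missing cap is why most H2 alpha goes before the FA.** The plan itself spends 63.5% by IA2. The omission affects only the excess.
- **H2 will have no final test.** That needs at least 415 events at IA2. About 373 are expected on the design assumptions.
- **H3 to H6 forfeit alpha at the FA.** The sentence "If events accrue more slowly than expected or the same as expected, spending will be based on actual information fraction" could be read so if their counts fall short. But the rule is introduced for interim timing, its worked example is IA1, and Table 15's final bounds use full alpha. This needs clarifying and is not a defect.

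**Conclusion.** The point holds as a cheap and worthwhile correction. H2 is left out of the cap for a reason that the trigger rules contradict. Interim spending can therefore run from the planned 63.5% to about 78%, 87% or 100% by IA2 in the scenarios tabulated. These figures rest on 415 as the H2 denominator, uniform accrual and the protocol's 2% dropout.

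The consequence is modest. It is about 1 to 2 power points (9-month median) or 4 points (8-month median) under the assumed delayed effect, about 2 to 3 points under proportional hazards when all alpha is gone by IA2, and very little if events accrue as planned. What is at risk is the purpose of the late FA. Validity and the stated power at HR 0.70 are not affected.

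**What to change.** In Section 8.7.2, apply the minimum of the actual and expected information fractions to H2 at IA1 and IA2, as for the other primary hypotheses, and name 415 as the H2 denominator if that is what is meant. As a separate minor clarification, state that the FA spends all remaining alpha for every hypothesis tested there, whatever its event count.

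The cost is a sentence or two of SAP text, to be settled before the next unblinded look. The downside is slightly stricter H2 interim bounds when events run ahead of plan. With 380/415/440 events, for example, the IA2 p bound would be 0.0070 instead of 0.0102, in exchange for an FA bound of 0.0111 where the present rule leaves none.

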**Overall Survival (OS)**

The non-parametric Kaplan-Meier method will be used to estimate the survival curves. The treatment difference in survival will be assessed by the stratified log-rank test for superiority hypotheses. A stratified Cox proportional hazards model with Efron's method of tie handling will be used to assess the magnitude of the treatment difference (ie, the hazard ratio). The hazard ratio and its 95% confidence interval from the stratified Cox model with a single treatment covariate will be reported. Geographic region, backbone therapy (5-FU or

Capecitabine) and disease status will be used as the stratification factors in both the stratified log-rank test and the stratified Cox model.

The non-inferiority hypothesis (H4) for pembrolizumab monotherapy vs. SOC will be evaluated using a stratified Cox regression model. The statistical criterion for the success of hypothesis H4 is that, if the upper bound of the confidence interval, based on the alpha level allocated to the analysis, for the hazard ratio (HR: monotherapy arm vs. control) is < 1.2, the pembrolizumab monotherapy arm could be considered as non-inferior to the control arm in terms of OS.

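### The smaller-fraction alpha-spending rule for H1 and H3 to H6 has no exception for the last look, so an event shortfall there leaves allocated alpha unspent (a conservative power loss, small on average)

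*Combined protocol and SAP*

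**What the plan says.** Section 8.7.2 treats H2 separately from the other primary hypotheses. H2's events trigger the analyses, and for it the plan says: "The boundary for the final analysis will be adjusted according to the actual alpha spent at the IAs".

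For H1, H3, H4, H5 and H6 the rule is different, "since the timing of the IAs are not driven by these hypotheses". Cumulative alpha follows the smaller of the actual and expected event fractions. If events run ahead, the expected fraction is used. If they run behind, "If events accrue more slowly than expected or the same as expected, spending will be based on actual information fraction". The stated purpose is to be no more aggressive than planned, "while at the same time ensuring that not all alpha is spent prior to final planned event counts". The one worked example is H3 at IA1 with too many events (125 against 111).

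The Table 15 bounds, which include the final-analysis rows, "will be updated at the time of the analyses using the observed number of events, the alpha re-allocation and spending functions as noted above". H1, H3, H5 and H6 use a Hwang-Shih-DeCani function with gamma -4. For H4 an "alpha-spending function with gamma parameter (-15) is used to construct group sequential boundaries".

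The triggers count only deaths in the combination and control arms. Table 15 sets IA2, the last look for H1, at 16 months after the last randomization and "at least 369 OS events are observed in the Combination arm and SOC arm, whichever comes later". The final analysis is set at 22 months and about 415 deaths in the same two arms.

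**The concern.** With fewer events than planned at a hypothesis's last look, the actual fraction is below 1. The rule as written then stops cumulative spending below the allocated alpha, and no later look exists to recover the rest. The relevant counts are 430 PFS events for H1 at IA2, and 147, 415, 415 and 148 deaths for H3, H4, H5 and H6 at the final analysis. None of these triggers an analysis, so each can fall short even when the trigger is met. Section 8.9 says the number of events is not subject to change, but that can hold only for the count that sets the timing.

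A primary hypothesis could therefore be tested at a stricter level than Section 8.8 allocates to it. The text also supports two different final boundaries. With 140 CPS10 deaths, an observed H3 hazard ratio of 0.65 fails under one and succeeds under the other. Section 3.1 lets a single significant primary hypothesis carry the trial, so the choice should not be left until the data are known.

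**Working it through.** **Inputs.** Alpha, hazard ratios, medians, accrual and dropout are from Section 8.9; event counts from Table 15; spending functions from Section 8.7.2. H4 power is taken at HR 0.82 (Section 8.9). Section 8.1 gives 0.8 for the same ~89%, but at 0.80 the power would be 93.0%.

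**Formulas.** Cumulative spending is a(t) = alpha × (1 − exp(−g·t)) / (1 − exp(−g)), with g = −4, or −15 for H4, and t = events / planned final events. Boundaries and power come from recursive integration with information = events/4. HR at the bound = margin × exp(−2z/√events), with margin 1.2 for H4 and 1 otherwise.

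**Step 1: reproduce the plan at its planned counts.**

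| | Last-look p | HR at bound | Table 15 HR | Power | Stated power |
|---|---|---|---|---|---|
| H1 | 0.0007 | 0.736 | 0.735 | 90.9% | ~91% |
| H3 | 0.0058 | 0.659 | 0.659 | 79.6% | ~80% |
| H4 | 0.00395 | 0.9245 | 0.925 | 89.0% | ~89% |
| H5 | 0.0030 | 0.763 | 0.763 | 82.4% | ~82% |
| H6 | 0.0058 | 0.660 | 0.661 | 79.9% | ~80% |

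For H4, for example, z = 2.6565 gives 1.2 × exp(−2 × 2.6565/√415) = 0.9245.

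**Step 2: fraction of alpha left unspent, 1 − a(t)/alpha.**

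| Shortfall | gamma −4 | gamma −15 (H4) |
|---|---|---|
| 1% | 4.0% | 13.9% |
| 2% | 7.8% | 25.9% |
| 5% | 18.5% | 52.8% |

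**Step 3: the rule as written against spending all remaining alpha at the last look** (interim counts as planned).

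For H3 at 140 deaths, t = 140/147 = 0.952. Cumulative spending is 0.0075 × 0.823 = 0.00618, so 17.7% of the alpha is unspent.

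| | Unspent | Last-look p: as written / all spent | Power: as written / all spent |
|---|---|---|---|
| H3, 140/147 (HR 0.58) | 17.7% | 0.0044 / 0.00625 | 74.9% / 77.7% |
| H6, 141/148 (HR 0.58) | 17.6% | 0.0044 / 0.0062 | 75.3% / 78.0% |
| H4, 411/415 (HR 0.82) | 13.5% | 0.0034 / 0.0040 | 87.6% / 88.6% |
| H4, 394/415 (HR 0.82) | 53% | 0.0018 / 0.0040 | 80.9% / 87.0% |
| H1, 425/430 (HR 0.65) | 4.6% | 0.0007 / 0.0008 | 90.2% / 90.5% |

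For H3 at 140 deaths the HR bounds are 0.643 and 0.656. H5 and H6 begin with 0% alpha, so they are affected only after reallocation.

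**Step 4: type I error.** Under the rule as written it equals the alpha actually spent. With a 3% shortfall this is 0.00671 of 0.00750 for H3 (143 deaths) and 0.00259 of 0.00400 for H4 (403 deaths).

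**Step 5: how likely a shortfall is.** The simulation used 2,000 trials per scenario, 250 patients per arm, uniform accrual over 19 months (assumed), Section 8.9 medians and dropout, OS HR 0.70 (combination) and 0.82 (monotherapy), and PFS HR 0.65. Each analysis occurs at the later of its month and its death count in the combination and control arms.

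- **H1:** mean 430.4 events, P(short) 45%; average loss 2.65% of alpha and 0.20 power points.
- **H4:** mean 427 deaths, P(short) 5.1%; average loss 0.7% of alpha and 0.06 points. Waiting for 415 combination and control deaths (median month 24.0) lets monotherapy deaths build up. A count as low as 394 arose in at most 1 in 2,000 trials per scenario.
- **H3:** the documents do not give the number of CPS10 patients. Assuming 147/(415/500) = 177 of 500, the CPS10 deaths among 415 are hypergeometric with mean 146.9, SD 4.0, P(short) 46% and P(140 or fewer) 6%. The average loss is 4.2% of alpha and 0.64 points; simulation gives 4.1% and 0.59.
- **H3 with HR 0.58 in CPS10 and 0.77 in the rest:** 182 CPS10 patients give a mean of 146.0 deaths and an average loss of 5.6% of alpha and 0.83 points; 177 give 141.8, 13.4% and 2.07 points.

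**The case against.** Two opposite readings can be pressed. The first is that the rule says what was meant: the plan wants to avoid spending all alpha before the planned event count is reached, and a final analysis that falls short has not reached it. Withholding alpha would then be deliberate. The second is that the rule concerns interims only. Its rationale is about interim timing, its example is IA1, and Section 8.6.1 judges H4 by a confidence interval "based on the alpha level allocated to the analysis". On that reading nothing is lost. Both have support in the text, and that is the difficulty. The rule carries no limit to interims, it feeds the final-analysis rows of Table 15, and the only sentence on a final boundary is for H2. Even that sentence does not say that all remaining alpha is spent.

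The stronger objection is to size, and it stands. The average losses are mostly below one point. The 45% chances of a shortfall for H1 and H3 arise mainly because the expected count sits close to the planned one, so most shortfalls are slight. The large H4 figures are tail events. The 2.1-point loss for H3 combines a back-calculated CPS10 number with an HR that lowers CPS10 deaths; the sponsor's actual CPS10 number could remove it.

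**Conclusion.** The concern holds, as a minor point. As written, the rule gives H1 and H3 to H6 a needlessly strict last-look boundary whenever their events fall short, and nothing elsewhere in the plan corrects this. The error is conservative. Small describes the average loss, or shortfalls up to about 2%, which cost roughly 2 points or less. It does not describe a 5% shortfall, which costs about 3 points for H3 and 6 for H4 at HR 0.82. The single-count results rest only on the plan's own figures. The averages also rest on uniform accrual, the Section 8.9 assumptions and, for H3, an assumed CPS10 number.

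**What to change.** Limit the smaller-fraction rule in Section 8.7.2 to looks before each hypothesis's last analysis, and add: at the final analysis of each hypothesis (IA2 for H1; the final analysis for H3 to H6), all remaining allocated alpha is spent, with the boundary computed from the alpha already spent and the actual event counts. Cumulative spending then equals the allocation, so type I error stays controlled. The same wording would usefully cover H2. If under-spending at the last look is intended, the plan should say so outright. The cost is one sentence by amendment before unblinding, with no extra patients or data.
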